5.2. Safety Analysis Set

The Safety Analysis Set is defined as all patients who receive at least one dose of Tofacitinib. This population will be used for all safety analysis.

5.3. Subgroups

The following subgroups will be considered for health resources and costs summaries and analyses. Cross-classification tables may also be presented combining the following subgroups depending on data availability.

Education Status

- Primary;
- Secondary; Tertiary (higher); Other.

Working Status

- Student;
- Part-time employed;
- Full time employed;
- Self-employed;
- Not working but looking for work;
- Not working not looking for work; Not working due to disability/illness; Retired.

Disease Severity

- **As defined by DAS28-4(CRP):**
- DAS28 >5.1 corresponds to a high disease activity;
- $3.2 \leq DAS28 \leq 5.1$ corresponds to a moderate disease activity;
 $2.6 \leq DAS28 < 3.2$ corresponds to a low disease activity; DAS28 value <2.6 corresponds to remission.

Treatment

- Tofacitinib as monotherapy;
- Tofacitinib in Combination with another DMARD; Other DMARD.
(See Section 11 A1.2 for definitions of DMARD).

PFIZER CONFIDENTIAL

Treatment Pattern

- Tofa mono;
- Tofa combo;
- Tofa mono to combo; Tofa combo to mono;
- Tofa to other treatment.

• **Co-morbidities**

- The three most common co-morbidities will be considered.

HAQ-DI at Baseline

- HAQ-DI at Baseline will be categorised as follows:
- <0.5 ;
- $[0.5-1.0)$;
- $[1.0-1.5)$;
- $[1.5-2)$;
- $[2-2.5)$; ≥ 2.5 .

EQ-5D at Baseline

- The following categories will be used:
- <0.4 ;
- $(0.4-0.6)$;
- $(0.6-0.8)$; $(0.8-1.0)$.

6. ENDPOINTS AND COVARIATES

6.1. Efficacy/Effectiveness Endpoint(s)

Baseline measurements for all endpoints are the last measurement before Tofacitinib treatment, up to 28 days before starting Tofacitinib. Change from baseline at a timepoint will be calculated as:

$$\text{Measurement at visit} - \text{Measurement at baseline}$$

6.1.1. Primary Endpoints

The primary endpoints are the rate of remission and low disease activity (LDA) at month 6 of treatment. These are assessed using the 28-joint Disease Activity Score C-reactive protein (DAS28-4 (CRP)), which is a composite endpoint, calculated using 4 variables (represented by '-4' in the name).

Remission and LDA are defined as DAS28-4 (CRP) <2.6 and DAS28-4 (CRP) <3.2 , respectively.

The DAS28-4 (CRP) will be calculated as follows:

PFIZER CONFIDENTIAL

$$\text{DAS28-4 (CRP)} = 0.56 * \sqrt{(\text{TJC})} + 0.28 * \sqrt{(\text{SJC})} + 0.36 * \ln(\text{CRP}+1) + 0.014 * \text{PtGA} + 0.96$$

Where CRP is in mg/l, TJC = tender joint count, SJC=swollen joint count, ln = natural logarithm and PtGA is the Patient's Global Assessment of Health in mm.

6.1.2. Secondary Endpoints

6.1.2.1. Remission or LDA at Month 12

The rate of remission and LDA at month 12 of treatment, assessed by DAS28-4 (CRP) < 2.6 and DAS28-4 (CRP) < 3.2, respectively. DAS28-4 (CRP) will be calculated as for the primary endpoint.

6.1.2.2. Change from baseline in DAS28-4 (ESR) and DAS28-4 (CRP)

The 28-joint Disease Activity Score erythrocyte sedimentation rate (DAS28-4 (ESR)) is a composite endpoint, calculated using 4 variables (represented by '4' in the name).

DAS28-4 (ESR) will be derived as follows:

$$\text{DAS28-4 (ESR)} = 0.56 * \sqrt{(\text{TJC28})} + 0.28 * \sqrt{(\text{SJC28})} + 0.70 * \ln(\text{ESR}) + 0.014 * \text{PtGA}$$

Where TJC = tender joint count, SJC=swollen joint count, ln = natural logarithm, ESR is measure in mm/ hour and PtGA is the Patient's Global Assessment of Health in mm.

DAS28-4 (CRP) is defined in [Section 6.1.1](#).

Change from Baseline in DAS28-4 (ESR) and DAS28-4 (CRP) will be calculated for each timepoint.

6.1.2.3. Change from Baseline in HAQ-DI

The Health Assessment Questionnaire – Disability Index (HAQ-DI) assesses the degree of difficulty a patient has experienced during the past week in 8 domains/categories of daily living activities: dressing and grooming, arising, eating, walking, hygiene, reach, grip, and other activities. Each activity category consists of 2-3 items. For each question in the questionnaire, the level of difficulty is scored from 0 to 3 with 0 representing "no difficulty," 1 as "some difficulty," 2 as "much difficulty," and 3 as "unable to do".

The HAQ-DI will then be derived using the Scaling and Scoring Guidelines v4.0 (July 2011). This can be found in [Section 11.2](#).

The HAQ-DI is calculated as follows:

- For each sub-category take the maximum score of all questions in that subcategory (score of 0-3).

PFIZER CONFIDENTIAL

- If aids were used for the sub-category a score of 0 or 1 is increased to 2 to more accurately represent underlying disability (scores of 3 are not modified).
- The average of the 8 categories is then calculated to obtain an overall HAQ-DI score of 0-3.

Section 7.1.1 provides the rules for deriving the HAQ-DI if there is missing data.

Change from Baseline in the HAQ-DI will be calculated for each time-point.

HAQ-DI will also be categorized using the subgroups outlined in Section 5.3.

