9.4.20. Health Assessment Questionnaire – Disability Index (HAQ-DI)

The HAQ-DI¹⁷ assesses the degree of difficulty a subject has experienced during the past week in 8 domains of daily living activities: dressing and grooming, arising, eating, walking, hygiene, reach, grip, and other activities. Each activity category consists of 2-3 items. For each question in the questionnaire, the level of difficulty is scored from 0 to 3 with 0 representing “no difficulty,” 1 as “some difficulty,” 2 as “much difficulty,” and 3 as “unable to do”. Any activity that requires assistance from another individual or requires the use of an assistive device adjusts to a minimum score of 2 to represent a more limited functional status. This questionnaire should be completed by the patient at each visit (visits 1-4) prior to any procedures being performed at the visit, if possible. The form should then be checked by the site staff for completeness.

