9.7.3.2.1. DAS28-4 (ESR), DAS28-4 (CRP), HAQ-DI

DAS28-4 (ESR), DAS28-4 (CRP) and HAQ-DI will be calculated at each time point as follows:

$$\text{DAS28-4 (CRP)} = 0.56*\sqrt{(\text{TJC28})} + 0.28*\sqrt{(\text{SJC28})} + 0.36*\ln(\text{CRP in mg/l} + 1) + 0.014*\text{PtGA in mm} + 0.96.$$

$$\text{DAS28-4 (ESR)} = 0.56*\sqrt{(\text{TJC28})} + 0.28*\sqrt{(\text{SJC28})} + 0.70*\ln(\text{ESR in mm/ hour}) + 0.014*\text{PtGA in mm}.$$

Where TJC is the Tender Joint Count, SJC is the Swollen Joint Count, CRP is the C-reactive protein in mg/L, ESR is the Erythrocyte Sedimentation Rate in mm/first hour and PtGA is the Patient's Global Assessment of Health in mm.

HAQ-DI ([Section 9.4.20](#)) score will be calculated at baseline and at each time point. The HAQ-DI is calculated by:

- For each sub-category take the maximum score of all questions in that sub-category (score of 0-3).
- If aids were used for the sub-category a score of 0 or 1 is increased to 2 to more accurately represent underlying disability (scores of 3 are not modified).
- The average of the 8 categories is then calculated to obtain an overall HAQ-DI score of 0-3.

The summary statistics of the absolute value and the change from baseline at each visit will be reported.

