6.1.2.6. HAQ-DI Response

A HAQ-DI response is defined as a decrease from baseline of at least 0.22 .

The percentage of patients achieving a HAQ-DI response at each time-point (month 3, 6 and 12) will be derived.

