6.4. Covariates

The following potential risk factors will be included as covariates in the logistic regression analyses of remission and LDA:

- Age:
Age at baseline will be included as a continuous covariate.
- Gender (male/female).
- Weight:
The weight (kg) at baseline will be included as a continuous covariate.
- Smoking history:
Smoking history will be included as a categorical covariate with five levels:
 - Never;
 - History but cessation of more than 3 years;
 - History but cessation of less than 3 years; Smoker, regular (≥ 1 cigarette/day); Smoker, low (< 1 cigarette/day).

If there are issues with the convergence of the model using the above categories, these will be collapsed into the following 3 categories:

- Never;
- Ex-Smoker; Smoker.

PFIZER CONFIDENTIAL

- Duration of Disease at Baseline:
Time (years) from RA diagnosis to inclusion in the study will be included as a continuous covariate.
- Serology at Baseline:
• Rheumatoid Factor (RF) will be included with two levels: positive and negative.
• Anti-citrullinated protein antibodies (ACPA) will be included with two levels: positive and negative.
- Previous DMARD use (number):
The number of previous biological (bDMARDs) will be included as a continuous covariate. See Appendix A1.2 for details of drugs to be considered as bDMARDs.
- Current concomitant treatment:
Two covariates will be fitted, one for the most common concomitant treatment (Yes/No) and one for the second most common concomitant treatment (Yes/No).
- Glucocorticoid dose:
The Glucocorticoid dose at baseline will be included as a continuous covariate.
- csDMARDs:
• The number of current conventional synthetic DMARDs (csDMARDs) at baseline will be included as a continuous covariate. See Appendix A1.2 for details of drugs to be considered as csDMARDs.
- The dose of csDMARDs at baseline will be included as a continuous covariate.
- Acute phase reactants:
ESR and CRP at baseline will be included as continuous covariates.
- DAS28-4 (CRP) score:
• DAS28-4 (CRP) at baseline will be included as a continuous covariate. This will be calculated as outlined in [Section 6.1.1](#).
- HAQ-DI score:
The HAQ-DI score at baseline will be included as a continuous covariate. This will be calculated as outlined in [Section 6.1.2.3](#).
- CDAI:
CDAI at baseline will be included as a continuous covariate. This will be calculated as outlined in [Section 6.1.2.4](#).
- Lipids:

PFIZER CONFIDENTIAL

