7.1.1. HAQ-DI

There must be responses in at least 6 of the 8 domains for a HAQ-DI score to be calculated. If there are 2 or more missing domains, the HAQ-DI will be set to missing. In the event that one or two domains have missing data, the score will be calculated by taking the average over the non-missing domains as follows:

HAQ-DI = Sum of non-missing domain scores/number of non-missing domains.

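### The rule that raises a HAQ-DI category to 2 is stated inconsistently: Protocol 9.4.20 counts help from another person, while the calculation steps in Protocol 9.7.3.2.1 and SAP 6.1.2.3 count aids only

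*SAP*

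**What the plan says.** Three places state the adjustment.

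- Protocol 9.4.20, describing the instrument, has two triggers: "Any activity that requires assistance from another individual or requires the use of an assistive device adjusts to a minimum score of 2".
- Protocol 9.7.3.2.1, giving the calculation, has one: "If aids were used for the sub-category a score of 0 or 1 is increased to 2".
- SAP 6.1.2.3 repeats the one-trigger step: "If aids were used for the sub-category a score of 0 or 1 is increased to 2 to more accurately represent underlying disability". It carries over most of the 9.4.20 description of the instrument, but not the sentence on help from another person.

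SAP 6.1.2.3 also names an outside source before listing its own steps: "The HAQ-DI will then be derived using the Scaling and Scoring Guidelines v4.0 (July 2011"). It refers the reader to Section 11.2, which the SAP contents list as the HAQ scoring guidelines. That text is not visible in the public document, and this is not a fault in the plan. Neither document says whether the guideline or the written steps prevail if they differ. SAP Section 1 declares no changes to the protocol analyses, so the narrower step is not presented as a deliberate modification.

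The score feeds several outputs: change from baseline; response (SAP 6.1.2.6: "A HAQ-DI response is defined as a decrease from baseline of at least 0.22"); HAQ-DI categories by visit; baseline HAQ-DI subgroups for the healthcare-resource summaries (SAP 5.3 and 8.2.4.1); and the remission and LDA models (SAP 6.4: "The HAQ-DI score at baseline will be included as a continuous covariate").

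**The concern.** Protocol 9.4.20 treats a helper and a device as two separate things. A programmer who follows the numbered calculation steps could therefore reasonably code devices alone. A patient who reports some difficulty in a category, has a relative's help and uses no aid would then score 1 in that category, where 9.4.20 gives 2. Two teams working from the same documents could produce different HAQ-DI values from the same form.

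At stake are the level of the score wherever it is used and, for some patients, whether they count as responders.

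**Working it through.** **Inputs.** Number of categories: SAP 6.1.2.3, "The average of the 8 categories is then calculated to obtain an overall HAQ-DI score of 0-3". Response threshold: a decrease of at least 0.22 (SAP 6.1.2.6). Minimum answered domains: SAP 7.1.1, "There must be responses in at least 6 of the 8 domains for a HAQ-DI score to be calculated". The documents give no frequency for personal help without an aid. No stated figure in the plan depends on this rule, so there is none to reproduce.

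**Size per category.** Let raw be the highest item score in a category. A flagged category scores max(raw, 2). For a category with personal help and no aid, the aids-only step leaves out (2 − raw) points if raw is 0 or 1, and nothing if raw is 2 or 3.

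| Domains averaged | Raw 1 | Raw 0 | Points needed for a 0.22 change |
|---|---|---|---|
| 8 | 1/8 = 0.125 | 2/8 = 0.25 | 0.22 × 8 = 1.76, so 2 |
| 7 | 1/7 = 0.143 | 2/7 = 0.286 | 0.22 × 7 = 1.54, so 2 |
| 6 | 1/6 = 0.167 | 2/6 = 0.333 | 0.22 × 6 = 1.32, so 2 |

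Two raw-1 categories, or one raw-0 category, are therefore enough to cross the response threshold.

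**Effect on change.** Let O be the amount left out at a visit (zero or more). Then:

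aids-only score = 9.4.20 score − O

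aids-only change = 9.4.20 change + (O at baseline − O at follow-up)

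The level can only be too low. The change can be wrong in either direction, and it is right when O is equal at the two visits.

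**Examples.** Eight categories, no aids, every category raw 1 unless stated.

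| Case | Aids-only steps | Protocol 9.4.20 | Result |
|---|---|---|---|
| A. Help in two categories at baseline, none later; raw scores unchanged | 8/8 = 1.00 to 8/8 = 1.00, change 0 | 10/8 = 1.25 to 8/8 = 1.00, change −0.25 | Response missed |
| B. Help in two categories at both visits; raw 1 falls to 0 in those two | 8/8 = 1.00 to 6/8 = 0.75, change −0.25 | 10/8 = 1.25 to 10/8 = 1.25, change 0 | Response falsely credited |
| C. Help in two categories at both visits; raw 1 falls to 0 in two other categories | 8/8 = 1.00 to 6/8 = 0.75, change −0.25 | 10/8 = 1.25 to 8/8 = 1.00, change −0.25 | Same under both |
| D. One raw-0 category, with help at baseline only | 7/8 = 0.875 to 7/8 = 0.875, change 0 | 9/8 = 1.125 to 7/8 = 0.875, change −0.25 | Response missed |
| E. Help only in categories with raw 2 or 3 | Same score | Same score | No effect |

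In case B the help is constant but the amount left out is not: O is 2/8 = 0.25 at baseline and 4/8 = 0.50 at follow-up. In case D the baseline score also changes band under SAP 5.3, from 1.0–1.5 under 9.4.20 to 0.5–1.0 under the aids-only step.

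**The case against.** The strongest reply is that SAP 6.1.2.3 says the score will be derived from the published guidelines, and the bullets may be no more than a short summary of them. If the guideline counts personal help and the programmer works from it, no score is understated. This stands, and it makes the numerical consequence conditional. It does not remove the inconsistency. Protocol 9.4.20 and 9.7.3.2.1 differ within one document, and nothing gives the guideline precedence over the steps written beneath it.

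A second reply is that the impact is modest. HAQ-DI change and response are secondary and summarised descriptively, and SAP Section 4 sets no formal hypotheses. Baseline HAQ-DI is one candidate among many and may not survive selection. DAS28-4 (CRP) does not use HAQ-DI. All of this stands.

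A reader might go further and infer that disability will be understated in the most dependent patients, that this happens more at baseline than later, and that real improvement is therefore hidden. The documents support none of this. Categories already scored 2 or 3 are identical under both rules, so the patients affected are those reporting no or some difficulty in a category who have personal help there and use no aid. Nothing is said about how help changes over time. Case B shows the error can also create improvement that 9.4.20 would not record.

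**Conclusion.** The inconsistency is certain on the face of the documents; its effect on results is conditional. It arises only if the aids-only steps are what is programmed, and only in categories with personal help, no aid and a raw score of 0 or 1. There the eight-category score is 0.25 or 0.125 below the Protocol 9.4.20 value. Response status changes only when the amount left out differs between visits by enough to cross 0.22, and it can change either way.

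Because the frequency of such categories is not given, no study-level bias can be stated, and none should be assumed. The reach is a secondary endpoint (change, response and categories), the baseline subgroups and one candidate covariate in the remission and LDA models. The primary outcome is untouched. It should be settled before programming because the correction is so small.

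**What to change.** 1. Reconcile Protocol 9.4.20, Protocol 9.7.3.2.1 and SAP 6.1.2.3 with the cited guideline. State explicitly whether help from another person triggers the adjustment, and which text governs if they differ.
2. Unless the guideline explicitly excludes personal help, amend the step in Protocol 9.7.3.2.1 and SAP 6.1.2.3 so that a sub-category score of 0 or 1 becomes 2 when an aid or device was used or when another person's help was needed.
3. Apply the settled rule at every visit and in every HAQ-DI derivation: baseline covariate, change, response, visit categories and baseline subgroups.
4. First confirm that the collected form holds the help items. The form is not shown in the documents, so this cannot be checked here.

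The cost is one sentence in each document and one line of derivation code. No new data are needed if the help items are on the form.

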6.1.2.4. Rate of Remission

Patient remission will be derived in four separate ways:

1. SDAI Remission

The Simplified Disease Activity Index (SDAI) will be derived at each time-point using the formula:

$$\text{SDAI} = (\text{TJC28}) + (\text{SJC28}) + \text{PhyGA} + \text{PtGA} + \text{CRP}$$

Where TJC = tender joint count, SJC = swollen joint count, PhyGA is the Physician's Global Assessment in cm, PtGA is the Patient's Global Assessment of Health in cm and CRP is C-reactive Protein in mg/dL.

SDAI Remission will then be derived as follows:

$$\begin{aligned} \text{SDAI_Remission} &= 1, && \text{if SDAI} \leq 3.3 \\ \text{SDAI_Remission} &= 0, && \text{otherwise.} \end{aligned}$$

The rate of remission based on SDAI will then be derived at month 3, 6 and 12.

2. CDAI Remission

The Clinical Disease Activity Index (CDAI) will be derived at each time-point using the formula:

$$\text{CDAI} = (\text{TJC28}) + (\text{SJC28}) + \text{PhyGA} + \text{PtGA}$$

Where TJC = tender joint count, SJC = swollen joint count, PhyGA is the Physician's Global Assessment in cm and PtGA is the Patient's Global Assessment of Health in cm.

CDAI Remission will then be derived as follows:

PFIZER CONFIDENTIAL

$$\begin{aligned} \text{CDAI_Remission} &= 1, & \text{if } \text{CDAI} \leq 2.8 \\ \text{CDAI_Remission} &= 0, & \text{otherwise.} \end{aligned}$$

The rate of remission based on CDAI will then be derived at month 3, 6 and 12.

3. DAS 28-4 (ESR) Remission

DAS 28-4 (ESR) will be derived at each time-point as outlined in [Section 6.1.2.2](#).

DAS 28-4 (ESR) Remission will then be derived as:

$$\begin{aligned} \text{DAS 28-4 (ESR)}_{\text{Remission}} &= 1, & \text{if } \text{DAS28-4 (ESR)} < 2.6 \\ \text{DAS 28-4 (ESR)}_{\text{Remission}} &= 0, & \text{otherwise.} \end{aligned}$$

The rate of remission based on DAS 28-4 (ESR) will then be derived at month 3, 6 and 12.

4. DAS28-4 (CRP) Remission

DAS 28-4 (CRP) will be derived at each time-point using the formula in [Section 6.1.1](#).

DAS 28-4 (CRP) Remission will then be derived as:

$$\begin{aligned} \text{DAS 28-4 (CRP)}_{\text{Remission}} &= 1, & \text{if } \text{DAS28-4 (CRP)} < 2.6 \\ \text{DAS 28-4 (CRP)}_{\text{Remission}} &= 0, & \text{otherwise.} \end{aligned}$$

The rate of remission based on DAS 28-4 (CRP) will then be derived at month 3, 6 and 12.

6.1.2.5. Rate of LDA

LDA for each patient will be derived in four separate ways:

1. SDAI LDA

SDAI will be derived at each time-point using the formula in [Section 6.1.2.4](#).

A patient is considered as having LDA if $\text{SDAI} \leq 11$.

The rate of LDA based on SDAI will then be derived at month 3, 6, 12.

2. CDAI LDA

CDAI will be derived at each time-point using the formula in [Section 6.1.2.4](#).

A patient is considered as having LDA if $\text{CDAI} \leq 10$.

The rate of LDA based on CDAI will then be derived at month 3, 6, 12.

3. DAS 28-4 (ESR) LDA

DAS 28-4 (ESR) will be derived at each time-point using the formula in section 6.1.2.2.

A patient is considered as having LDA if DAS 28-4 (ESR) <3.2

The rate of LDA based on DAS 28-4 (ESR) will then be derived at month 3, 6, 12.

4. DAS 28-4 (CRP) LDA

DAS 28-4 (CRP) will be derived at each time-point using the formula in section 6.1.1.

A patient is considered as having LDA if DAS 28-4 (CRP) <3.2

The rate of LDA based on DAS 28-4 (CRP) will then be derived at month 3, 6, 12.

6.1.2.6. HAQ-DI Response

A HAQ-DI response is defined as a decrease from baseline of at least 0.22 .

The percentage of patients achieving a HAQ-DI response at each time-point (month 3, 6 and 12) will be derived.

6.1.2.7. Change from Baseline in EQ-5D

The EQ-5D is a standardised instrument used to measure quality of life. It is based on five dimensions: mobility, self-care, usual activities, pain/discomfort and anxiety/depression. Each dimension has three responses and the patient is asked to select the response that best describes them. The responses are scored 1-3 as shown in [Table 2](#):

Table 2. EQ-5D

Dimension	Response	Score
Mobility	I have no problems in walking about	1
	I have some problems in walking about	2
	I am confined to bed	3
Self-care	I have no problems with self-care	1

	I have some problems washing or dressing myself	2
	I am unable to wash or dress myself	3
Usual activities (eg, work, study, housework, family or leisure activities)	I have no problems with performing my usual activities	1
	I have some problems with performing my usual activities	2
	I am unable to perform my usual activities	3
Pain/discomfort	I have no pain or discomfort	1
	I have moderate pain or discomfort	2
	I have extreme pain or discomfort	3
Anxiety/depression	I am not anxious or depressed	1
	I am moderately anxious or depressed	2
	I am extremely anxious or depressed	3

The score for each dimension is weighted in accordance with Table 3. These weightings are based on UK data (Dolan et al 1995).

Table 3. EQ-5D weightings

EQ-5D Dimension	Score = 1	Score = 2	Score = 3
Mobility	0	0.069	0.314
Self-Care	0	0.104	0.214
Usual Activities	0	0.036	0.094
Pain/Discomfort	0	0.123	0.386
Anxiety/Depression	0	0.071	0.236

The following algorithm is then applied to calculate the EQ-5D Total Score:

PFIZER CONFIDENTIAL

1. If **all** five EQ-5D dimensions have a score of 1 then the EQ-5D Total Score is 1.
2. If **any** of the five EQ-5D dimensions have a score of 3, then the EQ-5D Total Score is:

$$1 - 0.081 - \left(\sum_1^5 \text{weighted dimension score} \right) - 0.269$$

3. If **none** of the five EQ-5D dimensions has a score of 3, then the EQ-5D Total Score is:

$$1 - 0.081 - \left(\sum_1^5 \text{weighted dimension score} \right)$$

Missing weighted dimension scores are imputed as outlined in [Section 7.1.2](#).

The EQ-5D score will be derived for all time points and the change from baseline calculated.

The EQ-5D score at each visit will also be categorised into the following subgroups:

- <0.4;
- (0.4-0.6];
- (0.6-0.8];
- (0.8-1.0].

